However there is a key difference in the clinical populations found in the literature, surgeons have an operative team and are not responsible for patient monitoring while operating. Likewise anaesthetists are usually accompanied by an ODP and are not undertaking practical skills in isolation.

We were not able to find any published literature addressing attention and perception during ICU procedures.

What does this research add?

There is no published experimental data investigating how clinician time perception and attention are impacted by performing tasks in an IC environment. There is an expectation that time perception and attention are preserved, such that clinicians can insert central access as a sole practitioner. Should our investigation show that attention is impacted then this could inform changes to practice as to how monitors and/or additional staff members are utilised during procedures and clinical tasks and how practitioners are trained to undertake them.

AIM(S) OF STUDY

- To investigate the relationship between task type, perceptual loading and attention in an ICU environment
- To investigate the relationship between task type, perceptual loading and time perception in an ICU environment
- To examine if the extent of these effects (if any) are affected by clinician role and/or experience

OBJECTIVES

The objective of this study is to measure clinician awareness of time progression and monitoring trends in the clinical environment during 2 different types of task.

HYPOTHESIS

H₀: Task type has no impact on clinician time perception or awareness of monitoring trends.

H_A: In the technical task clinician time awareness is more inaccurate than in the administrative task

H_B: In the technical task clinician awareness of monitoring trends is impaired compared to in the administrative task

STUDY DESIGN

STUDY SETTING/LOCATION

This will be a single-centre study undertaken in the Intensive Care Units at Great Ormond Street Hospital. The study tasks will be run in the simulation room on the general Paediatric ICU.

STUDY POPULATION

Participants will be recruited from the group of ICU junior/senior tier fellows and Consultants working on the ICUs at Great Ormond Street Hospital. This comprises a pool of around 40 staff members. All staff members are routinely involved in the care of patients in a PIC environment.

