Randomisation	Randomisation of task order and monitor trend scenario: increasing/decreasing
Timing control task	To assess baseline time perception for each participant
Break	To reset and brief the participant for the first task
First task	Administrative or technical task depending on randomisation

Monitor scenario in first task	The parameters do not change aside from a brief desaturation at 30 seconds into the task, to orient participants to the monitor within the task
Break	To reset and brief the participant for the second task
Second task	Administrative or technical task depending on randomisation
Monitor scenario in second task	There is a desaturation at 30 seconds as before to orient participants to the monitor within the task. The blood pressure then either falls or rises, depending on the randomisation, settling at the final value at 4 minutes. The change in blood pressure only occurs in the second task so as to allow immediate review of trend awareness, this is not possible to do after the first task without introducing bias in the second task.
Post task review	To check immediate recall of monitor trends in the second task. Asked immediately to reduce the impact of recall/memory bias on the answers.
Questionnaire	Provides quantification of any trend in parameters noticed.
Debrief	To answer queries and identify any areas of participant support required.

Experimental scenarios:

Each participant will undertake the timing control task first and then both the administrative and technical tasks, the order of these determined by the randomisation table.

1. Timing control

The participant sits and is asked to push a foot pedal every 10 seconds with no reference to external timekeeping. This task continues for 6 minutes.

Participants are instructed: "Please press the foot pedal every 10 seconds, trying to be as accurate as possible. The task will last for several minutes."

After 6 minutes the participant will be asked for the time period they believe has elapsed between the first pedal press and the last.

2. Administrative task:

Request investigations for a new admission

Equipment required:

- PIMS-TS investigations pack
- Computer signed in to the EPIC learning environment for a dummy patient
- Simulated bedside monitor
 - Varies observations over time in line with preset programming determined by the study team
- Foot pedal and data recorder for time logging

Setup

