All equipment laid out on a table. The tissue pad is attached to the mannequin leg and surgically draped appropriately. The ultrasound probe is already in a sterile sheath, lying on the sterile field.

Instructions to subject

You are the fellow/consultant looking after Sophie. Sophie is a 2 year old girl with PIMS-TS. She is intubated and is stable on minimal ventilation and peripheral noradrenaline of 0.1mcg/kg/min. She has just been admitted to the unit. This is Sophie's bedspace, all the equipment you see is part of the simulation.

Your task is to request the admission investigations according to the sheet provided.

The nurse looking after the patient has had to step out of the bedspace to prepare their infusions and have asked you to complete your task whilst keeping an eye on the patient in the bedspace.

I am the nurse in the next bedspace, if at any point you want to make a clinical intervention please continue with the task and verbalise anything you would like me to do.

As before, when I ask you to begin, please press the foot pedal every 10 seconds, trying to be as accurate as possible. The task will last for several minutes.

Events during the task:

If this task is the first task undertaken, then the bedside monitor will display the same values throughout, aside from 1 desaturation. Heart rate: 125 bpm, blood pressure: 90/50 (65), respiratory rate: 25, oxygen saturations: 98%, end tidal CO₂: 4.5 mmHg. The oxygen saturation measure will fall to 88% for 5 seconds at 30 seconds into the task, triggering an alarm. This is to orient the participant to the monitor being part of the environment.

Normal values for age are: Heart rate: 80-140 bpm, respiration rate: 20-28 (APLS), 5th centile systolic: $65+(2 \times 2)=69$, 5th centile MAP: $50+(2 \times 2)=54$.

At 30 seconds into the task there will be a 10 second desaturation to 88% with spontaneous normalisation to 98%.

If this is the second task undertaken then values on the monitor will change during the task.

There are 2 monitor scenarios, 'A' and 'B'. Allocation between these is determined in the randomisation table (see appendix). They are identical apart from 'A' being a falling trend and 'B' a rising trend

- Scenario A
 - The oxygen saturation measure will fall to 88% for 5 seconds at 30 seconds into the task, triggering an alarm. This is to orient the participant to the monitor being part of the environment.

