You have been asked to insert a femoral CVC and have already prepared your equipment.. The line is not flushed. You are already wearing the appropriate sterile gown. Please only use steristrips and dressings, with no sutures, to secure the line to the mannequin. Please document the procedure on the paper provided when you have completed insertion of the line.

I am the nurse in the next bedspace, if at any point you want to make a clinical intervention please continue with the task and verbalise anything you would like me to do.

As before, from when I ask you to begin, please press the foot pedal every 10 seconds, trying to be as accurate as possible. The task will last for several minutes.

Given that this is a simulated mannequin please take all the time you need to familiarise yourself with the ultrasound appearance of the vessels before telling me you are ready to begin.

Events during the task:

Same as for the administrative task.

End point

6 minutes or completion of task documentation.

At the end of the task, progress through the checkpoints below will be noted by the experimenter:

1. Equipment preparation / line flushing
2. Cleaning of the procedure site
3. Initial ultrasound scan
4. Needle manipulation
5. Guide wire insertion
6. Tract dilation
7. Line insertion
8. Line suturing
9. Line dressing
10. Documentation completed

The participant will be asked for the time period they believe has elapsed between the first pedal press and the last.

Post- task review

Following completion of the second task the participant will immediately be asked the following questions:

“Did you see anything of note on the monitor aside from the desaturation” - their yes/no answer is recorded.

“If there were changes in the blood pressure did you notice a fall or a rise” - their rise/fall answer is recorded.

Was the extent of the fall/rise in systolic pressure: 5, 10,15, 20 or 25 mmHg- their selection is recorded.

Which of the tasks did you find more challenging? And why?

They are then asked to describe their subjective experience- “how were those tasks for you?”

They are then asked- “How would you describe your familiarity with EPIC order requesting?”- Very, somewhat, limited, none

They are then provided with the questionnaire from the appendix.

Measurement tools used

- For each experimental run there are 2 variables
 - The task order- administrative or technical completed first

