 - Correct identification of no trends in other parameters - reported as proportion of participants correct
 - Accuracy of magnitude recall
 - The blood pressure either falls or rises between a systolic/diastolic (mean) of 70/48 (55) and 90/50 (65).
 - From the position of the x on the linear blood pressure scales we can derive:
 - The accuracy of the initial and final estimates compared with the actual values- reported for each task as the population mean and standard deviation of the percentage errors compared with the actual value.
 - The accuracy of the magnitude of the change, determined through comparing the difference in the estimated initial and final values compared with the actual 20mmHg systolic/ 10mmHg diastolic change for each task. The population mean and standard deviation of the percentage errors compared with the actual change will be reported for each task.
 - We hypothesised that there would be a priming effect following administration of the questionnaire, with participants more likely to attend to blood pressure trends if the questions were asked prior to the second task. We will therefore only ask the questions after the second task. We can then compare between the subgroups, split by which of the tasks was performed second to examine the impact of task type.
 - i.e the questionnaire analysis will have half the n of the overall study
- For the above we can compare subgroups using Fishers exact test.
 - By task order
 - By grade
 - By number of CVCs previously inserted

- By first 25% vs last 25% of participants

STATISTICAL CONSIDERATIONS AND DATA ANALYSIS

Sample size and statistical power

This is a pilot study and as such we do not expect it to be adequately powered to confirm hypotheses but intend that it should be hypothesis generating.

Statistical methods

The population summary statistics detailed above will be calculated using 'SPSS statistics' software with built-in min/max/mean/IQR/SD calculation.

With assumed normally distributed timing data and each participant completing 2 tasks the distributions will be compared with a paired sample t-test for; control vs administrative, control vs technical and administrative vs technical. For subgroup analysis paired or unpaired sample t-tests will be used as appropriate in each case. For the trend perception outcomes, contingency tables will be created for each subgroup and compared using Fishers exact test.

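### Only the administrative script asks the participant to watch the patient, so part of any trend-awareness gap favouring H_B could come from the briefing rather than the task

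*Combined protocol and SAP*

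**What the plan says.** The administrative task's Instructions to subject include two linked statements: "The nurse looking after the patient has had to step out of the bedspace to prepare their infusions", and that the participant has been "asked you to complete your task whilst keeping an eye on the patient in the bedspace".

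At the corresponding point, the technical task's Instructions to subject go straight to the procedure: "You have been asked to insert a femoral CVC and have already prepared your equipment". They do not say where the bedside nurse is and contain no request to watch the patient.

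The Structure table states that "The change in blood pressure only occurs in the second task". It also gives both tasks the same early alarm: "There is a desaturation at 30 seconds as before to orient participants to the monitor within the task".

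H_B reads: "In the technical task clinician awareness of monitoring trends is impaired compared to in the administrative task". Under Monitor trend perception analysis, participants are to be compared "split by which of the tasks was performed second to examine the impact of task type", using Fisher's exact test. Accuracy of trend recall is listed as a primary outcome.

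On sample size the plan says only that this is a pilot and that "we do not expect it to be adequately powered to confirm hypotheses". No section explains the difference between the scripts or allows for it in the analysis.

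**The concern.** A request to watch the patient bears directly on whether a monitor change is noticed. It belongs to one script only, and the outcome is measured only in the second task. The administrative-second group therefore hears it immediately before the drift, and the technical-second group does not. If the request does anything, it should raise noticing in the administrative-second group, which is the direction H_B predicts.

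Randomising task order does not help, because the sentence travels with the task. Nor can the analysis recover the separate effects, since nobody performs the technical task with the sentence in its script.

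The stake is interpretation. Under Outcomes and Significance, the protocol says that marked impairment during a technical procedure would point to the need for an assistant and to policy changes on monitoring. A gap produced partly by the briefing would be read as an effect of task load.

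**Working it through.** **1. The scripts side by side**

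| Element | Administrative | Technical |
|---|---|---|
| Participant is the patient's responsible doctor | Yes | Yes |
| Stable on low-dose peripheral noradrenaline | Yes | Yes |
| Bedside nurse said to be absent | Yes | No |
| Request to watch the patient | Yes | No |
| Neighbouring nurse; invitation to voice interventions | Yes | Yes |
| Orienting desaturation at 30 seconds | Yes | Yes |
| Central access needed for inotropes | No | Yes |

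The inotrope clause is a secondary mismatch: it gives the indication for the line, and both scripts already mention noradrenaline. The appendix holds a shorter administrative instruction without the request. If only that were read out, the tilt would not arise.

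**2. What each group has heard when the drift begins**

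- Administrative second: the request, in the current briefing.
- Technical second: the request, but in the earlier briefing for the other task, before the break.

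So the groups differ in how recent the request is and in which task it is attached to. Let w be the rise in noticing from a current request, and c the fraction of that rise that survives from the earlier task. The net cue is

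d = w(1 − c).

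Full carry-over (c = 1) gives d = 0. With half carry-over, a raw effect of 20 points gives d = 20 × (1 − 0.5) = 10 points.

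**3. Inputs for an illustration**

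The plan gives no sample size, significance level, noticing rate or cue size, so it has no figure to reproduce.

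- From the documents: Study Population gives a pool of around 40. The appendix randomisation list has 10 administrative-first and 10 technical-first in each of two strata, so 2 × 10 = 20 per group is the ceiling.
- Assumed: no true task effect; two-sided 5% level; noticing p_T = 50% in the technical-second group; p_A = p_T + d; 10 or 20 per group.

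**4. Chance of a significant result favouring H_B**

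Sum over all outcomes (i, j) of Bin(i; n, p_A) × Bin(j; n, p_T), keeping those with Fisher p ≤ 0.05 and i > j.

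| Net cue d | 20 per group | 10 per group |
|---|---|---|
| 0 (matched scripts) | 1.0% | 0.6% |
| 5 points | 2.3% | 1.2% |
| 10 points | 4.7% | 2.0% |
| 20 points | 16.3% | 5.4% |

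Fisher's test is conservative at these sizes. The smallest whole-point cue that takes the figure above a nominal 2.5% in one direction is 6 points at 20 per group (2.64%) and 13 points at 10 per group (2.74%).

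The assumed noticing rate matters little. With a 10-point cue and p_T of 30%, 50% or 70%, the figures are 5.7%, 4.7% and 6.1% at 20 per group, and 2.0% each time at 10 per group.

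**5. Chance of an observed gap of at least 20 points favouring H_B**

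A pilot is read mainly through its observed gap. The 20-point mark is chosen here for illustration and is not in the plan.

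| Net cue d | 20 per group | 10 per group |
|---|---|---|
| 0 (matched scripts) | 13% | 25% |
| 5 points | 21% | 33% |
| 10 points | 32% | 41% |

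The top row is sampling noise alone. The excess attributable to a 10-point cue is 32 − 13 = 19 percentage points at 20 per group, and 41 − 25 = 16 at 10 per group.

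**The case against.** The best defence is that the contrast is weak. Everyone has heard the request once, about the same patient, before the drift begins. Both groups then get an identical audible alarm at 30 seconds, just as the drift starts, which is a more recent and more specific monitor cue than a sentence about the patient in general. Both scripts invite voiced interventions. The inotrope clause, found only in the technical script, could draw attention to blood pressure and push the other way. Every probability above rests on assumed rates, and the study claims only to generate hypotheses.

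Much of this stands. It makes a small net cue more plausible than a large one, and for a small cue the excess of false positives is slight or nil. It does not remove the asymmetry. The alarm equalises the display, not the instruction. Only complete carry-over makes the bias zero, and nothing in the documents establishes that. The inotrope clause states why a line is needed and asks nobody to watch anything, so it is a weaker prompt than a direct request, although the documents size neither.

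A further objection is that adding the request to the technical script changes the question, by prompting an operator who would otherwise be unprompted. That is a fair cost. It bears on which way to match the scripts, not on whether to match them.

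**Conclusion.** The concern holds, as a minor point. The two briefings are not matched on an element that bears directly on a primary outcome. The mismatch is tied to task type in the second task and would be expected to favour H_B by an unknown, diluted amount.

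A net cue of 5 points or less leaves the false-positive chance in that direction under 2.5% at either group size. A 10-point cue takes it to 4.7% at the 20-per-group ceiling and 2.0% at 10 per group. The observed gap is affected more than the test. If the request has no effect, or carries over in full, nothing changes. These sizes depend on the assumed noticing rate and cue, and on the main-text script being the one read out.

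**What to change.** Before recruitment, put the identical nurse-absence and watch-the-patient sentence in both scripts. This suits the sole-practitioner question raised under What does this research add. Omitting it from both would remove the bias equally well. In the same edit, use one shared patient paragraph, which also settles the inotrope clause, and bring the appendix instruction into line with the main text.

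With matched scripts the wording contributes nothing to the task contrast, and the test returns to the zero-cue row of the working.

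The cost is a one-sentence change to one script plus the shared paragraph, with no extra time, staff or data. The briefing becomes slightly less task-specific. Adding the sentence may also raise absolute noticing in the technical task above that of an unprompted operator. Leaving it out of both scripts avoids that second cost, but removes the stated reason why a doctor ordering tests is responsible for watching the patient.

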 - The blood pressure will fall from an initial systolic/diastolic (mean) of 90/50 (63) at 30 seconds to 75/48 (55) at 4 minutes and then remain static at that level. There will be no alarm. This gradual drift tests participants' awareness and identification of monitoring trends during the task through what point they notice a change, if they do at all.

- Other parameters (heart rate, respiratory rate, oxygen saturations, end-tidal CO₂ and temperature) will not vary.
- Scenario B
 - The oxygen saturation measure will fall to 88% for 5 seconds at 30 seconds into the task, triggering an alarm. This is to orient the participant to the monitor being part of the environment.
 - The blood pressure will rise from an initial systolic/diastolic (mean) of 75/48 (55) at 30 seconds to 90/50 (63) at 4 minutes and then remain static at that level. There will be no alarm. This gradual drift tests participants' awareness and identification of monitoring trends during the task through what point they notice a change, if they do at all.
 - Other parameters (heart rate, respiratory rate, oxygen saturations, end-tidal CO₂ and temperature) will not vary.

End point:

6 minutes or completion of the task.

The participant will be asked for the time period they believe has elapsed between the first pedal press and the last.

3. Technical task

Inserting a CVC.

Equipment required:

- Child mannequin, intubated
- CVC insertion mannequin
- US machine + gel + probe cover
- CVC set
- Syringes, flush
- Cleaning- chlorprep lollipops
- Suture, needle holders, scissors, sharps bin
- Dressings + biopatch
- Gloves (non-sterile)
- Drape
- 5 +10ml syringes
- Sterile field drape
- Pen and paper for documentation
- Simulated bedside monitor
 - Varies observations over time in line with preset programming determined by the study team
- Foot pedal and data recorder for time logging

Setup

All equipment laid out on a table. The tissue pad is attached to the mannequin leg and surgically draped appropriately. The ultrasound probe is already in a sterile sheath, lying on the sterile field.

Instructions to subject

You are the fellow/consultant looking after Sophie. Sophie is a 2 year old girl with PIMS-TS who requires central access for inotropes. She is intubated and is stable on minimal ventilation and peripheral noradrenaline of 0.1mcg/kg/min. This is the Sophie's bedspace, all the equipment you see is part of the simulation

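### The blood pressure values used to score trend recall, a primary outcome, do not match the values programmed on the monitor; the two scenarios also differ in more than direction

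*Combined protocol and SAP*

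**What the plan says.** Study Outcomes lists accuracy of retrospective trend recall as a primary outcome.

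**Display.** Under Events during the task (administrative task), the first-task monitor is static: "Heart rate: 125 bpm, blood pressure: 90/50 (65), respiratory rate: 25". For the second task, scenario A reads "The blood pressure will fall from an initial systolic/diastolic (mean) of 90/50 (63) at 30 seconds to 75/48 (55) at 4 minutes" and scenario B reads "The blood pressure will rise from an initial systolic/diastolic (mean) of 75/48 (55) at 30 seconds to 90/50 (63) at 4 minutes". Of the pair it says "They are identical apart from 'A' being a falling trend and 'B' a rising trend". For the technical task the events are "Same as for the administrative task", so the display does not depend on task order.

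**Intent.** The Structure table states that "The change in blood pressure only occurs in the second task". It describes the break as "To reset and brief the participant for the second task" and the post-task review as "To check immediate recall of monitor trends in the second task".

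**Scoring.** Monitor trend perception analysis gives the range as 70/48 (55) to 90/50 (65). It compares recalled change with an actual change of 20 mmHg systolic and 10 mmHg diastolic. The appended questionnaire asks for initial and final systolic and mean pressure; it has no diastolic item. The Post-task review asks for the size of the systolic change as 5, 10, 15, 20 or 25 mmHg. The planned subgroup comparisons do not include scenario.

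**Allocation.** The Randomisation section says the scenario is randomised. The printed list alternates A and B down all 20 rows, in one column that serves both grades.

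**The concern.** Percentage errors and proportions correct mean something only if the answer key is what the participant saw. Here the display section and the analysis section give different keys, and part of the analysis key (diastolic) has no matching question. An analyst who follows the plan literally would report error in participants who made none. An analyst who chooses between the keys after seeing the data makes an unplanned choice on a primary outcome.

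A second, softer worry is that A and B mirror each other only within task 2. Seen across the session, A runs 90, 90, 75 systolic and B runs 90, 75, 90. Because the recall items do not say which task they refer to, a scenario B answer given relative to task 1 could be marked wrong, while the same habit in A would cost almost nothing.

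**Working it through.** **1. Reproducing the stated change of 20/10.** Inputs are the end values in the two sections.

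| Source | Systolic | Diastolic | Mean |
|---|---|---|---|
| Events during the task | 90 - 75 = 15 | 50 - 48 = 2 | 63 - 55 = 8 |
| Monitor trend perception analysis, its own end values | 90 - 70 = 20 | 50 - 48 = 2 | 65 - 55 = 10 |
| Monitor trend perception analysis, stated change | 20 | 10 | not stated |

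The 20 follows only from the analysis section's values. The diastolic 10 follows from neither section; it equals the analysis section's change in mean.

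**2. Scoring a perfect reading of the programmed display against the analysis section.** Error = (answer - key) / key.
- Systolic change: (15 - 20)/20 = -25%.
- Lower systolic value: (75 - 70)/70 = +7.1%.
- Upper mean value: (63 - 65)/65 = -3.1%.
- Verbal size item: the correct option is 15 by one section and 20 by the other.
- Diastolic change: not computable, because no diastolic answer is collected.

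These errors arise in both scenarios and need no assumption about behaviour.

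**3. Can arithmetic show which set was meant?** Using the usual approximation, mean = diastolic + (systolic - diastolic)/3: 90/50 gives 63.3, 75/48 gives 57.0 and 70/48 gives 55.3. The display section's 63 agrees but its 55 does not fit 75/48. The analysis section's 55 agrees but its 65 does not fit 90/50. Neither set is right throughout, so the simulator programme itself has to settle it.

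**4. Step from task 1 to the start of task 2.** Task 1 is 90/50 (65).
- A: systolic 90 - 90 = 0; mean 63 - 65 = -2.
- B: systolic 75 - 90 = -15; mean 55 - 65 = -10. If the analysis section's 70 were displayed, the systolic step would be -20.
- The scored systolic trend in B is +15 (or +20): equal in size and opposite in sign.

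The second-task display for seconds 0 to 30 is not stated, so where a participant would see this change is not fixed.

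**5. What an answer relative to task 1 would cost**, keyed to the display section:
- B, marking 90 to 90: initial systolic (90 - 75)/75 = +20%; initial mean (65 - 55)/55 = +18.2%; systolic change (0 - 15)/15 = -100%.
- A, same habit: initial systolic 0%; initial mean (65 - 63)/63 = +3.2%; systolic change 0%.

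Let q be the share of otherwise-correct B participants who answer this way, with half of all participants in B. The pooled proportion correct is then multiplied by 1 - q/2. An assumed q of 10% gives a 5% relative loss, and 50% gives 25%. The documents give no value for q.

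**6. The list**, if each grade uses numbers 1 to 20 in sequence. Falling:rising among Consultants is 6:4 administrative-first and 4:6 technical-first; among Others it is 5:5 and 5:5. The totals are 11:9 and 9:11, a difference in falling share of 0.55 - 0.45 = 0.10. Stopping at 10 + 10 gives 7:3 v 3:7, the worst case among stopping points with at least 16 participants. In 50,000 simulated lists with scenario blocked separately from order, a difference of at least 0.10 occurred in 78%, so the alternation is not what produced it.

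**The case against.** On the scoring values, one may say that these are slips of drafting and that any analyst would use the values shown. That is likely, but the analysis section presents its figures as the actual change, and nothing in the documents says which set the simulator runs. The conflict stands.

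On scenario B, the opposing case is strong. The questions come immediately after task 2. The first verbal question mentions a single desaturation, and each task has exactly one. The verbal direction item is a forced choice of fall or rise, so a no-change answer is possible only on the written form. Someone who noticed the rise has an obvious answer. Someone who marks 90 to 90 may simply have missed the drift, and marking that wrong is what the test intends. A break and a new briefing come between the tasks, and the administrative briefing describes the child as just admitted. Against this, both tasks concern the same child on the same infusion, the written items use *overall* and *initial* without naming a task, and results are not split by scenario. What stands is an ambiguity of unknown size.

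Three stronger readings are tempting and should not be drawn:
- **That the task comparison is biased.** The step occurs in both task orders. It would distort the comparison materially only if answering across tasks depended on which task came first, and the documents give no evidence on that.
- **That a diastolic error of (2 - 10)/10 = -80% will be reported.** It cannot be, since diastolic pressure is not collected.
- **That the alternating list introduces a systematic bias.** Its imbalance is modest and due to chance.

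The study is a hypothesis-generating pilot. That excuses low power, but it does not excuse an inconsistent answer key.

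**Conclusion.** The plan is wrong as written on the answer key for a primary outcome. Against the programmed display, a faultless participant receives -25% on systolic change, the lower systolic value differs by 5 mmHg between sections, the correct verbal option is undetermined, and the stated diastolic change matches neither the displayed values nor any question asked. This rests only on the documents' own figures.

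The scenario asymmetry is secondary. The 15 mmHg systolic step in B alone is a fact of the programmed values, so the scenarios are not alike apart from direction across the session. Its effect on pooled recall accuracy is unknown; the 5% to 25% range above is illustration under assumed shares, and prompt questioning probably keeps it small. A reader might infer that reasonable B answers are in fact being marked wrong in numbers, but the documents show only that this could happen.

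The list is a minor matter: its alternation does not match the description of the scenario as randomised. The 11:9 v 9:11 split assumes separate numbering within each grade.

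**What to change.** 1. Reconcile Events during the task and Monitor trend perception analysis to one set of simulator values (lower systolic 75 or 70; mean at 90/50 63 or 65, which also differs between task 1 and task 2). Score against the values actually displayed, and state the correct verbal option.
2. Replace the diastolic change in the analysis with the change in mean, which the questionnaire already collects.
3. Tie every verbal and written recall item to the second task, and ask for the initial value at the start of the second task.
4. State the second-task display for seconds 0 to 30.
5. Report recall by scenario alongside the pooled figures.
6. Either regenerate the list so that each block of 4 within a grade holds the four order-by-scenario combinations in random order, or describe the scenario as alternated.

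Changing the pressures is optional. Matching the task 1 pressure to each participant's task 2 start makes the task 1 display differ by scenario. A common start with opposite changes gives up the mirrored end values. Each removes one asymmetry and introduces another.

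The cost is edited text and question wording, a check of the simulator programme, one extra table and, if chosen, a new list. No added participants, staff or visits are needed.
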